3.2 Randomization

Subjects will be randomly assigned to use either the test or control solution. Two codes will be used for the test product and one code for the control so there are equal numbers of bottles of each code ('A', 'B' or 'C'). Subjects will also be randomly assigned to a lens type.

A random number generator (Microsoft Excel) will be used to determine the randomization of solutions and lens types. Each eligible subject will randomly be assigned to one of the lens care products and lens types using a blocking method and stratified by site. All sites will use both the test and control solutions. Each site will only use four of the six study lens types.

The randomization will be performed in stages. Firstly, the sites will be randomly assigned to four of the six study lens types. Secondly, subjects will be randomly allocated, by site, to one of the four lens types in blocks of four subjects. Thirdly, subjects within each site and lens type will be randomly allocated to one of the three solution codes (2 x Test, 1 x Control) in blocks of three subjects.

Subject ID numbers will be assigned consecutively to maintain randomization.

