3.1 Masking

To prevent bias, several steps will be taken to keep the investigators and subjects masked to the identity of the assigned solution:

- Subjects will be identified by subject numbers, which are unrelated to study solution assignments.
- Solution bottles will be over-labelled ('A', 'B' or 'C') and packaged in kit-boxes so that the identity of the study solution is not revealed. Therefore, investigators must only dispense solutions for the study that have been provided by the sponsor or clinical research organisation (CRO).
- If for any reason the investigator needs to be unmasked to the solution type that the study subject is using, they should follow the decoding procedures which will be present in the investigator study binder.

If required, for purposes of a subject's safe clinical management, the investigators will be able to learn the identity of the solution being used by contacting the study Clinical Research Associate (CRA).

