4 STUDY POPULATION

4.1 Number of Sites

Approximately ten sites located in the UK and the US each recruiting approximately 20 subjects/site (up to a maximum of 24 subjects/site). Investigators will be contact lens practitioners with at least three years' post-registration experience of contact lens practice.

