4.2 Number of Subjects

Approximately 200 subjects will be enrolled in the study. Of these, approximately 133 subjects will use the test solution (Oté Sensation) and 67 subjects will use the control solution (Bausch & Lomb BioTrue).

Each subject will be required to attend up to four scheduled study visits over a period of approximately 1 month.

Subjects will be currently adapted soft contact lens wearers and will be recruited from the sites' existing patient database or via REC/IRB approved recruitment material. The anticipated enrolment period for the study is approximately 5 weeks.

The study population has been chosen to represent the range of patients that may use this multipurpose solution type.

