7.5 Visit 1b: Lens Fitting and Dispensing

The subjects will undergo a trial fit with the randomly allocated study lens type. If the appropriate study lenses are not available, a dispensing visit will be scheduled for another day.

- i. Slit lamp – confirm continued eligibility if on a different day
- ii. Record the parameters of the lenses on the Dispensing eCRF (lens type / lot number, lens parameters, etc.).

The performance of the lenses should be assessed after 10-15 minutes settling time and the following variables will be assessed:

- iii. Subjective comfort (0-10)

- iv. Vision
 - Monocular HC DVA (with CL)
 - Spherical over-refraction (SOR)
 - Monocular HC DVA with SOR
 - Binocular distance VA with CLs (Snellen/logMAR to the nearest letter)
- v. Surface characteristics
 - Lens surface wetting (0-4) and reason if Grade 1 or less.
- vi. Lens fit
 - Centration (0-2)
 - Corneal coverage (Y/N)
 - Post-blink movement (0-4)
 - Tightness on push-up (0-4)
 - Overall fit acceptance (0-4) and reason if Grade 2 or less.

To be successfully dispensed, subjects must show >Grade 2 lens fit acceptance with the trial lens and must be correctable to 6/12 (20/40) (0.30 LogMAR) or better in each eye. Trial lenses must also show >Grade 1 wettability.

Modifications to optimize the lens power will be allowed.

If the lens fit is acceptable, the investigator will issue the care system (Kit-box containing solution, lens case and instructions) that the subject was randomized to, and complete the Kit-box Accountability Log. All kit-boxes must be accounted for, even if they are not dispensed.

- vii. The subject will be instructed to wear the lenses on a daily wear basis (at least 8 hours a day, 6 days per week) until the 1-week follow-up appointment, unless they experience a problem which warrants lens removal. In this case the subject should contact the investigator.
- viii. The investigator or a clinical assistant will review the Participant Information Guide with the subject, which describes the procedures for contact lens wear, lens care, handling, cleaning and disinfecting. Any subject, who does not follow instructions to a degree that, in the Sponsor or Investigator's opinion, jeopardizes the subject's wellbeing or the validity of the study, will be discontinued.
- ix. The investigator will complete the Source Document Record (Appendix 3).

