11.5 Source Documentation

The eCRFs will be considered the source document, unless otherwise documented. The sponsor's representatives (Visioncare Research) will be authorized to gain access to the source documentation for the purposes of monitoring and auditing the study (see sections 11.6 and 11.7).

The Source Document Record must be completed to comply with GCP guidelines. It is a permanent record within the patient's records/notes that documents the subject's involvement in a clinical research study.

Contents of the source document record:

- Study number
- Subject ID
- Confirmation that subject met eligibility criteria
- Confirmation that subject signed the informed consent
- Confirmation that subject received a signed and dated copy of informed consent
- Date enrolled
- Details of Solution (code) assigned
- Details of lenses worn on study
- General notes
- Adverse events
- Exit date
- Whether subject completed the study or discontinued
- Investigator's signature

The Source Document Record will be completed for each subject upon enrolment and then updated when required, e.g. when subject exits the study.

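### Section 3.2 prints one fixed block size of three per site and lens type while code letters are visible at site, so future solution codes are partly predictable; varying the blocks is a cheap improvement

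*Combined protocol and SAP*

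**What the plan says.** Section 3.2 randomises in stages. Sites are first given four of the six lens types. Next, "subjects will be randomly allocated, by site, to one of the four lens types in blocks of four subjects". Then, within site and lens type, subjects are "randomly allocated to one of the three solution codes (2 x Test, 1 x Control) in blocks of three subjects". The letters are common to the whole trial: "Two codes will be used for the test product and one code for the control". The section names Excel as the random number source and consecutive subject IDs as the safeguard for the sequence. It does not mention varying block sizes, central allocation, custody of the list or any other concealment step.

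Section 3.1 masks the product, not the letter: "Solution bottles will be over-labelled ('A', 'B' or 'C') and packaged in kit-boxes". The letter also goes into the site's own file. Section 11.5 lists "Details of Solution (code) assigned" among the contents of the Source Document Record, and the Appendix 3 template has a field for it. Section 4.1.1 requires investigators to be trained on the protocol, so they will have read the block sizes.

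On timing, Section 7.4 assigns lens type and solution after the eligibility checklist. The trial fit and issue of the kit-box follow in Section 7.5.

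**The concern.** Each block of three contains A, B and C once. An investigator who keeps track of letters by lens type knows the third letter of a block after seeing the first two, and can guess the second better than chance. Allocation concealment is meant to prevent this kind of foresight when the next wearer is approached for consent.

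A letter alone is harmless to the comparison. It would matter if a site learned or inferred which letter is the control. With only three letters in the trial, decoding one control subject, which Section 3.1 permits for safe clinical management, reveals the control letter for every subject. The lens cases also differ by brand (Section 5.1, Table 1), and the masking steps in Section 3.1 mention bottles and kit-boxes but not the case. The risk is then selective enrolment: the choice of whom to enrol next could depend on the expected solution.

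**Working it through.** **Plan's figures.** 180 completers / (1 − 0.10) = 200. 200 × 2/3 = 133.3 and 200 × 1/3 = 66.7, which reproduces "approximately 133 subjects will use the test solution (Oté Sensation) and 67 subjects will use the control solution". Section 4.1 gives about 20 subjects per site, at most 24. Over four lens types this is 20/4 = 5 or 24/4 = 6 per site-by-lens stratum. The documents give no figure for predictability.

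**Assumptions.** The site tracks past letters by lens type, and every subject takes the next slot (no slots lost to screen failures). For the varying blocks, the investigator is taken to know that each stratum is 3+3 or 6 with equal chance, which is the worst case.

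**Fixed blocks, lens type known.**
- Letter: slot 3 of each block is certain. 1/5 = 20% (about 40 of 200); 2/6 = 33%.
- Arm, control letter known: slot 2 is certain if slot 1 was control (1/3), and slot 3 always. (1/3 + 1 + 0 + 1/3)/5 = 33%; (2 × 4/3)/6 = 44%.
- Arm, only one test letter known: the arm is certain only when that letter is the last left in the block (1/3 per complete block). (1/3)/5 = 6.7%; (2/3)/6 = 11.1%.
- Arm, no letter known: 0%.

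**Fixed blocks, before lens type is drawn.** Lens blocks of four mean that subjects 1–4 take slot 1 of their strata, subjects 5–8 slot 2, subjects 9–12 slot 3, and so on. With k lens types left in the lens block, the prediction is certain only if all k agree.
- Letter: subjects 9–12 (k = 4, 3, 2, 1) give 1/27 + 1/9 + 1/3 + 1 = 1.48. 1.48/20 = 7.4%. At 24 per site the same occurs at subjects 21–24: 2.96/24 = 12.3%. The average chance of guessing the letter is 47% to 51%, against 33% by chance.
- Arm, control letter known: subjects 5–8 give 1/81 + 1/27 + 1/9 + 1/3 = 0.49. Subjects 9–12 give 17/81 + 27/81 + 45/81 + 1 = 2.10. At 20 per site: (0.49 + 2.10 + 0.49)/20 = 15.4%. At 24: 2 × 2.59/24 = 21.6%.

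**Varying blocks (3+3 or 6), lens type known.**
- Letter: a block of six has 90 sequences. In 18 of them the first four slots exhaust two letters, so slot 5 is certain (18/90 = 0.2). Such a history cannot arise under 3+3, so the average is 0.5 × 0.2 = 0.1. Slot 6 is always certain. 0.1/5 = 2%; 1.1/6 = 18.3%.
- Arm, control letter known: slots after the second control are certain, and slot 5 is certain if slots 1–4 held no control. Over slots 1–5 this gives 3/9 = 0.333 under 3+3 and (3 + 4 + 3 + 1)/15 = 0.733 under 6, average 0.533. 0.533/5 = 10.7%; (0.533 + 1)/6 = 25.6%.

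**Varying blocks, before lens type is drawn (letter).** Subjects 17–20 give 0.1 + 0.1²/3 + 0.1³/9 + 0.1⁴/27 = 0.103, so 0.103/20 = 0.5%. Subjects 21–24 add 1.48, so 1.585/24 = 6.6%.

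| Certain prediction | Fixed 3, at 5 / 6 per stratum | 3+3 or 6, at 5 / 6 per stratum |
|---|---|---|
| Letter, before lens type | 7.4% / 12.3% | 0.5% / 6.6% |
| Letter, lens type known | 20% / 33% | 2% / 18% |
| Arm, control letter and lens type known | 33% / 44% | 11% / 26% |

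**Balance.** At 5 per stratum both schemes give 1 control with probability 1/3 (a control sits in slot 6: 1/3 under 3+3, 2/6 under 6) and otherwise 2. At 6 both give exactly 2. For a stratum that stops at 3, fixed blocks give exactly 1 control. A block of six gives 0, 1 or 2 with probabilities 4/20, 12/20 and 4/20, so the mixture gives 0.1, 0.8 and 0.1.

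**The case against.** The case on the other side is substantial and limits the point in several ways.

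- **Timing.** A reader might infer that the last code of every block is known when a subject is enrolled. It is not. Lens type is drawn first, and both assignments follow eligibility, so the 20% and 33% do not apply at the enrolment decision; the 7% and 12% do.
- **Lens fit.** Section 7.5 says "To be successfully dispensed, subjects must show >Grade 2 lens fit acceptance with the trial lens", and a reader might infer that fixed blocks let an investigator steer at this step. The subject's code is already assigned by then, so any exposure there is the same with every block size, and varying the blocks does not change it. It is a separate matter.
- **Any decoded letter.** A reader might apply 33% to 44% whenever one letter is known. Those figures need the control letter. Two of the three letters are test letters, and knowing one of them gives 6.7% to 11.1%.
- **Detection.** It would be too strong to say that nothing planned could show selection. Section 10.2 reports descriptive statistics by solution at baseline, and every consented subject is accounted for (Sections 7.1 and 7.5.4). A gross imbalance might show there, although no planned test is aimed at it.
- **Lost slots.** IDs are given at consent (Section 7.4), while Section 3.2 speaks of eligible subjects. If the list is keyed to ID, screen failures use up unseen slots and predictability falls. The documents do not settle this.
- **Speculation.** Bias needs a site to identify the control letter, keep track of codes, and act on them. The documents show none of this.

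All of these stand as limits. None removes the basic fact: one small block size, printed for investigators, with visible letters and no further concealment step described.

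**Conclusion.** The point holds as a modest weakness in allocation concealment. The letter is certain for about 7% to 12% of subjects at the enrolment decision and for 20% to 33% once lens type is known. If the control letter became known, the arm would be certain for about 15% to 22% and 33% to 44% respectively. The ranges run from 20 to 24 subjects per site and assume that no slots are lost to screen failures.

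The documents do not support the stronger inference that the non-inferiority comparisons are biased. Product identity is masked, and the size of any bias depends on investigator behaviour that the documents do not describe. It is zero if no one acts on a prediction. The label is a cheap improvement.

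**What to change.** In Section 3.2, replace the fixed block of three with permuted blocks of randomly varying size: 3+3 or 6, chosen at random in each site-by-lens stratum, keeping two test codes to one control code. Remove the block sizes of both the lens and the solution stage from the protocol that sites receive, and record them in a randomisation document held by the CRO.

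The cost is a regenerated list and one edited paragraph before enrolment, with no extra subjects, kits or staff. The 2:1 balance is unchanged at 5 or 6 per stratum. The small downside is that a stratum stopping early, for example at 3, may be slightly less balanced. The change reduces predictability but does not abolish it, and it leaves the three trial-wide letters in place.

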4 STUDY POPULATION

4.1 Number of Sites

Approximately ten sites located in the UK and the US each recruiting approximately 20 subjects/site (up to a maximum of 24 subjects/site). Investigators will be contact lens practitioners with at least three years' post-registration experience of contact lens practice.

4.1.1 Investigator Recruitment

Investigational sites will be identified by Visioncare Research. The Investigators will be required to fulfil the following criteria:

- Appropriately licensed eye care practitioner or contact lens optician
- At least three years, post-registration contact lens fitting experience.
- In-office email.
- Willingness to follow the study protocol and to co-operate with the study monitors.
- Experienced investigators trained in Good Clinical Practice (GCP) and the study protocol prior to commencing the study.
- Computers available to complete CRFs using electronic data capture (EDC).

All of the investigational sites will be trained and evaluated by on-line training modules before enrolling subjects.

This clinical study is designed to be in conformance with the ethical principles in the Declaration of Helsinki, with the ICH guidelines for GCP and all applicable local regulations.

4.2 Number of Subjects

Approximately 200 subjects will be enrolled in the study. Of these, approximately 133 subjects will use the test solution (Oté Sensation) and 67 subjects will use the control solution (Bausch & Lomb BioTrue).

Each subject will be required to attend up to four scheduled study visits over a period of approximately 1 month.

Subjects will be currently adapted soft contact lens wearers and will be recruited from the sites' existing patient database or via REC/IRB approved recruitment material. The anticipated enrolment period for the study is approximately 5 weeks.

The study population has been chosen to represent the range of patients that may use this multipurpose solution type.

4.3 Inclusion Criteria

Subjects must satisfy the following conditions prior to inclusion in the study:

- i. Be a currently adapted soft contact lens wearer (>1 month of lens wear).
- ii. Be at least 18 years of age.
- iii. Refractive astigmatism ≤ 0.75 D in both eyes.
- iv. Have clear corneas and be free of any anterior segment disorders.
- v. Be correctable through spherocylindrical refraction to 6/12 (20/40) (0.30 LogMAR) or better in each eye.
- vi. Contact lens sphere requirement between +4.00D and -8.00D (inclusive).
- vii. Require visual correction in both eyes (monovision allowed, no monofit).
- viii. Have normal eyes with no evidence of abnormality or disease. For the purposes of this study a normal eye is defined as one having:
 - a. No amblyopia
 - b. No strabismus
 - c. No evidence of lid abnormality or infection
 - d. No conjunctival abnormality or infection that would contraindicate contact lens wear
 - e. No clinically significant slit lamp findings (i.e. corneal staining, stromal edema, staining, scarring, vascularization, infiltrates or abnormal opacities)
 - f. No other active ocular disease.

4.4 Exclusion Criteria

Any of the following will render a subject ineligible for inclusion:

- i. Require toric or multifocal contact lenses.
- ii. Previously shown a sensitivity to any of the study solution components.
- iii. Any systemic or ocular disease or allergies affecting ocular health.
- iv. Using systemic or topical medications that will in the investigator's opinion affect ocular physiology or lens performance.
- v. Clinically significant (\geq Grade 3) corneal staining, corneal stromal edema, corneal vascularization, tarsal abnormalities, bulbar hyperemia, limbal hyperemia, or any other abnormality of the cornea that would contraindicate contact lens wear.
- vi. Any corneal infiltrates or any corneal scarring or neovascularization within the central 5mm of the cornea.
- vii. Keratoconus or other corneal irregularity.
- viii. Aphakia or amblyopia.
- ix. Have undergone corneal refractive surgery or any anterior segment surgery.

- x. Abnormal lacrimal secretions.
- xi. Has diabetes.
- xii. Known/reported infectious disease (e.g., hepatitis, tuberculosis) or an immunosuppressive disease (e.g., HIV).
- xiii. History of chronic eye disease (e.g. glaucoma).
- xiv. Pregnant or lactating or planning a pregnancy at the time of enrolment.
- xv. Participation in any concurrent clinical trial or in last 30 days.

4.5 Subject Identification

Subjects will be identified by a four-digit code made up of the site number and their enrolment number.

The enrolment ID **must** be assigned to the subjects sequentially. Enrolment numbers will be in ascending order for each site. Thus, the first subject to be enrolled at Site 1 will be 01/01, the second 01/02 and so forth. The first subject to be enrolled at Site 2 will be 02/01, the second 02/02 and so on. No ID can be used more than once and enrolment is recorded on the Enrolment Log (Appendix 1).

4.6 Study Withdrawal Criteria

If during the study it becomes evident to either the Sponsor or the Clinical Research Organisation (Visioncare Research) that the study test solution (Oté Sensation) poses a threat to subject well-being, the study will be terminated. The REC/IRB will be advised of the reason for termination.

4.7 Subject Replacement

Subjects that are discontinued or drop out of the study will not be replaced.

4.8 Subject Compliance

To track compliance, subjects will be questioned at each of the follow-up visits about: their lens cleaning regimen, average contact lens wearing times (typical insertion and removal times), average number of days lenses are worn per week and their contact lens solution usage.

Subjects will also be asked to return their remaining solution at the end of the study.

5 MATERIALS

5.1 Study Solutions

The contact lens care systems that will be used in this study are recorded in Table 1. The solutions will be over-labelled and secured in kit-boxes.

Table 1: Care Product Details

	Test	Control
Brand	Oté Sensation	Bausch & Lomb BioTrue®
Manufacturer	Oté Pharma, [name]	Bausch & Lomb U.K., Ltd. [name]
Disinfectant	polyaminopropyl biguanide 0.00002%, polyquaternium-2 0.0001%	polyaminopropyl biguanide 0.00013%, polyquaternium-1 0.0001%
Wetting and other agents	sodium hyaluronate	hyaluronan, sulfobetaine, poloxamine, boric acid, sodium borate, EDTA
Bottle size	300 or 360 ml	
Lens case	Oté lens case	B&L lens case
CE Mark	Yes	Yes

Subjects will be given a leaflet explaining the care system regimen and instructions. A rub and rinse step is included in the required regimen for both the test and control multipurpose solutions.

The solution bottles will be over-labelled and the subjects and investigators will be masked to the solution type.

Both solutions will be provided to the sites in sealed kit-boxes by the sponsor's representative (Visioncare Research) and all boxes containing the study care solutions must be fully accounted for.

5.2 Concomitant Care Products and Medications

Subjects must only use the care products issued by the Investigator. Subjects will be instructed to use no other lens care products (e.g. daily cleaner solution or protein remover), unless absolutely necessary. If rewetting drops are required, investigators should dispense preservative-free, unit dose wetting drops (e.g. AMO Blink™ Contacts Vials). All unused solutions (empty, unopened or partially used bottles) will be returned to the investigator during Visit 3.

All medications (prescription and over the counter) that the subjects are taking at enrolment will be documented on the eCRF at baseline, including supplements such as vitamins and minerals, and/or herbs taken by the participant.

5.3 Study Contact Lenses

Subjects will be randomly allocated to use one of six lens types (Table 2). Approximately 33 subjects will be allocated to use each lens type: approximately 22 using the test MPS product and 11 using the control product.

Each investigational site will use four of the six lens types (e.g. Types 1,2,3,4 or Types 1,2,5,6 or Types 3,4,5,6). Each site will utilise a stock of lenses so that, where possible, subjects may be dispensed lenses at the first visit. However, if the appropriate lenses are not immediately available, a second visit (Visit 1b) will be scheduled.

One of the lenses (Acuvue 2) is recommended for 2-weekly replacement. For these subjects, spare lenses will be issued during the Baseline visit with instructions for replacement.

In the event of lens loss or damage, replacement lens(es) will be issued at an unscheduled visit.

Table 2: Contact Lens Details

	Type 1	Type 2	Type 3	Type 4	Type 5	Type 6
Brand	ACUVUE® 2	PureVision®	Clariti	ACUVUE® VITA®	Air OPTIX®	Biofinity®
Manufacturer	Johnson & Johnson Vision Care	Bausch & Lomb	CooperVision	Johnson & Johnson Vision Care	Alcon	CooperVision
Material type	Conventional hydrogel	SH ionic, plasma oxidation surface treatment	SH non-ionic, not surface treated, high water	Silicone hydrogel (SH) non-ionic, not surface treated; contains PVP	SH non-ionic, surface modification by plasma polymerization	SH non-ionic, not surface treated; contains monomer n-vinyl pyrrolidone
Material	etafilcon A	balafilcon A	somofilcon A	senofilcon C	lotrafilcon B	comfilcon A
Water content	58%	36%	56%	41%	33%	48%
FDA Group	Group 4	Group 5A	Group 5B	Group 5Cr	Group 5Cm	Group 5C
Base curve / Diameter (mm)	8.30, 8.70 / 14.0	8.60 / 14.0	8.40 / 14.1	8.40 / 14.0	8.60 / 14.2	8.60 / 14.0
Replacement period	2-weekly	Monthly	Monthly	Monthly	Monthly	Monthly
Powers (D)	+4.00 to -8.00					

